## **4.0 STUDY PLAN**

#### 4.1 STUDY SCHEMA

#### 4.2 Study Procedures

##### 4.2.1 Enrollment/Recruitment

We will recruit 50 medically stable patients who have undergone conventional head CT imaging for imaging within 5 days with the s-HCT system. We will recruit medically stable patients with head trauma or known intracranial hemorrhage (subdural or intraparenchymal) or skull fractures with recent CT imaging. Subjects will be serially recruited with the assistance of the neurosurgery department at our institution. If the attending physician deems a patient stable, a clinical coordinator will obtain informed consent from the subject. If the coordinator has questions about patient competency to provide informed consent, a qualified healthcare provider will make the appropriate determination. In some cases, patients may have recently suffered from a trauma and may be seen for a follow up appointment. In these cases, the s-HCT scan may be obtained prior to the follow up head CT as long as it meets the 5 day window.

Given our high institutional volume of ruptured brain aneurysms and our Level I trauma status, we do not anticipate difficulty with patient volume.

Participants' involvement is limited to one single visit, which will include the s-HCT scan. No follow-up is necessary.

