#### 4.2.4 Reader Study

All images will be de-identified before inclusion within a reader study. We will perform a reader study with physician readers comparing the acquired imaging s-HCT images and conventional head CT. We hypothesize that the sensitivity of reader's in the interpretation of images from the s-HCT system will be similar to that of the conventional CT imaging. The paired images will be presented to five readers. Readers will be blinded to which imaging modality is being presented. There is, however, readers may be able to distinguish the imaging modality based on the images. Our readers will consist of a trauma surgeon, neurosurgeon or neuro radiologist and non-study radiologists to better reflect the different clinical backgrounds that may be available in a Role 3 environment.

Reconstructed images will be presented in a clinical PACS environment. The readers will be presented images for interpretation in a two-phase study with an interim washout period. First, for each patient, either the s-HCT or conventional head CT images will be presented in random order, and the readers will be asked to identify the presence of hemorrhage (yes/no), the location of the pathology if present and confidence level (0 through 100% in 10% increments). Readers will also be asked to perform interpretations with the appropriate Imaging CT CDE, including the Marshall CT TBI classification code 30, hemorrhage and fracture elements. Four weeks later, the other modality for each patient will be presented in a random order and the same scoring obtained.

The scoring scheme used by readers will include 1) hemorrhage (yes/no) with confidence 0-100% in 10% increments, 2) fracture (yes/no) with confidence 0-100% in 10% increments, 3) streak artifacts (yes/no), and ) other artifacts (yes/no).

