### 7.3 Data Analysis Plans

We will estimate the sensitivity and specificity from the two modalities. To compare the results from the two imaging modalities, we will adopt the mixed effect ANOVA based on the Dorfman-Berbaum-Metz method. To test the main hypothesis, the F-test statistic from the model parameter estimates will be used to compare the mean sensitivity / specificity metrics between the conventional head CT and the simulated solid-state head CT. Possible interactions between the modalities and the readers and the hemorrhage type/locations will also be included and tested for statistical significance. Sensitivity and specificity on the presence of clinically actionable pathology will also be assessed, based on consensus read of the conventional imaging.

For each confidence comparison, the average confidence scores and the corresponding standard deviations will be reported. To test whether the mean

confidence score is larger than zero, a linear mixed effect will be used to analyze data, where the outcome variable is the confidence scores collected in this study and only a grand mean parameter is in the independent list. Additionally, a random intercept is used in the model to account for the correlation among readers when reading the images from the same patient. The Wald's test based on model fit will be used to test whether the grand mean parameter is larger than zero. When the p-value from this test is less than 0.05, it will be concluded that there exists significant evidence that readers have more confidence with the s-HCT modality compared to the other modality. ROC curves will be evaluated.

We will also descriptively compare inter-reader agreement by modality for image quality, confidence in image interpretation, presence and location of hemorrhage, and presence and location of fractures by computing and reporting Fleiss' kappa.

All statistical estimates of population parameters will be tabulated along with corresponding confidence intervals (CIs) and/or standard errors (SEs) to convey levels of precision / imprecision. Hypothesis tests that are deemed to be not statistically significant will be indicated as inconclusive.

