## 11.0 APPENDICES

**READER STUDY:** Evaluation of a Carbon Nanotube Enabled Solid-State Head CT

Subject ID: \_\_\_\_\_

Reader: \_\_\_\_\_

Date: \_\_\_\_\_

1) Hemorrhage: \_\_\_\_\_ Yes \_\_\_\_\_ No  
Hemorrhage confidence 0-100% in 10% increments: \_\_\_\_\_ %  
Location (lobe): \_\_\_\_\_

2) Fracture: \_\_\_\_\_ Yes \_\_\_\_\_ No  
Fracture confidence 0-100% in 10% increments: \_\_\_\_\_ %  
Location (bone): \_\_\_\_\_

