## 5. Sum score (+1): \_\_\_\_\_

## 6. Image Quality

1	2	3	4	5
Non-interpretable; Artifact present;	Artifact present; moderately interferes with	Artifact present; mildly interferes with interpretability	Artifact present; does not interfere with	High quality, no artifacts

severely interferes with interpretability	interpretability		interpretability	
---	------------------	--	------------------	--

7. Streak Artifacts:  Yes  No

Location (lobe): \_\_\_\_\_

8. Other artifacts:  Yes  No

Location (lobe or  
bone): \_\_\_\_\_

Reader comments regarding the images:

---

---

Reader comments regarding artifacts:

---

---

---

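### Unweighted Fleiss' kappa is planned for two ordered scores, reader confidence (11 levels) and image quality (1-5), and it cannot tell a one-step disagreement from an extreme one

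*Combined protocol and SAP*

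**What the plan says.** Section 7.3 (Data Analysis Plans) names one agreement statistic for every reader item. The sentence opens "We will also descriptively compare inter-reader agreement by modality for image quality, confidence in image interpretation", goes on to the hemorrhage and fracture items, and ends "presence and location of fractures by computing and reporting Fleiss' kappa".

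Two of these items are ordered scales:

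- **Confidence.** The reader form in section 11.0 asks for "Hemorrhage confidence 0-100% in 10% increments" and uses the same scale for fracture. Section 4.2.4 describes the same scale. The levels are 0, 10, ..., 100%, which makes 11. On the form the reader first answers yes or no, then gives the percentage.
- **Image quality.** The form item headed "6. Image Quality" runs from 1 (not interpretable) to 5 (no artifacts).

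The size of the exercise comes from section 4.2.4, "The paired images will be presented to five readers", and section 4.2.1, "We will recruit 50 medically stable patients". The documents specify no weights, intraclass correlation, ordinal alpha or collapsing of categories. Elsewhere in section 7.3 confidence is treated as a number, with means, standard deviations and a linear mixed model.

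**The concern.** Fleiss' kappa is a nominal statistic. It asks whether two readers chose the same category and ignores how far apart they are. That suits the yes/no items and the location items. On an ordered score it treats 90% versus 100% confidence as the same failure as 0% versus 100%.

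The readers are deliberately drawn from different specialties, so small differences in how they use a percentage scale are plausible. Someone judging a new device needs to know whether readers differ by one artifact grade or disagree on whether the image can be read at all. The planned coefficient cannot show which, for either modality. Fixing the statistic before the reads are analysed also avoids a later switch that could look driven by the result.

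**Working it through.** The documents give no kappa value, target or precision, so there is no stated figure to reproduce. The check has two parts.

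**1. Response to distance**

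Fleiss' kappa = (P - Pe) / (1 - Pe). P is the share of reader pairs within a patient that match exactly. Pe is the sum of squared overall category proportions.

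Suppose the five readers split 3 versus 2 in every patient:

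- P = (3 x 2 + 2 x 1) / (5 x 4) = 0.40, whatever the gap.
- With 11 levels used equally, Pe = 1/11 = 0.091, and kappa = (0.40 - 0.091) / (1 - 0.091) = 0.34. In samples of 50 patients the levels are used a little unevenly, and the simulated mean is 0.33 for gaps of 1, 3 and 5 steps.

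Quadratic-weighted kappa = 1 - Do/De. Do is the mean squared difference between readers of the same patient. De is the mean squared difference between any two ratings, which is twice the pooled variance. Here 12 of 20 ordered pairs differ, so Do = 0.6 x gap squared.

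Assume case values spread evenly over steps 0-10 (mean 5, mean square 35), with the two dissenting readers placed the stated gap above, or below where the scale ends. If those two readers have mean M and mean square S, the pooled variance is 0.6 x 35 + 0.4 x S - (0.6 x 5 + 0.4 x M)².

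| Gap (steps) | M | S | Pooled variance | Do | De | Weighted kappa | Simulated, 50 patients |
|---|---|---|---|---|---|---|---|
| 1 | 5.818 | 42.364 | 9.57 | 0.6 | 19.13 | 0.97 | 0.96-0.97 |
| 3 | 6.364 | 44.545 | 8.07 | 5.4 | 16.13 | 0.67 | 0.63-0.66 |
| 5 | 5.455 | 37.273 | 9.06 | 15.0 | 18.12 | 0.17 | 0.15-0.17 |

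On the 5-level image quality scale the same split gives a simulated Fleiss' kappa of 0.23 for a gap of 1 or 2 steps. The weighted kappa falls from 0.82 to 0.27.

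**2. How low Fleiss' kappa reads when scores nearly agree**

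This depends on how often readers miss exact agreement, which the documents do not give. Assumptions: 50 patients, five readers, and each read either at the case value or one step off, with errors truncated at the ends of the scale. The case mix is also assumed. Cells show Fleiss' kappa / two-way random-effects ICC for absolute agreement, as means over at least 500 simulated data sets. In these runs the quadratic-weighted kappa lies within about 0.01 of the ICC.

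| Score and assumed case values | 10% of reads off | 20% | 50% | 67% |
|---|---|---|---|---|
| Confidence, all 11 levels | 0.81 / 0.99 | 0.65 / 0.98 | 0.36 / 0.95 | 0.31 / 0.94 |
| Confidence, 70-100%, weighted to the top | 0.79 / 0.92 | 0.60 / 0.85 | 0.27 / 0.68 | 0.20 / 0.60 |
| Confidence, 90 or 100% only | 0.72 / 0.75 | 0.52 / 0.58 | 0.15 / 0.29 | 0.08-0.09 / 0.20 |
| Image quality, all five levels | 0.81 / 0.96 | 0.65 / 0.92 | 0.34 / 0.81 | 0.27 / 0.75 |
| Image quality, 3-5 | 0.77 / 0.87 | 0.57 / 0.76 | 0.21 / 0.52 | 0.15 / 0.43 |

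Across these rows Fleiss' kappa is about 0.72-0.81 at 10% scatter, 0.52-0.65 at 20%, and 0.08-0.36 at 50-67%.

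**The case against.** The strongest reply is that little hangs on this. Section 7.3 calls the comparison descriptive, agreement is not among the objectives in sections 2.1 and 2.2, and no threshold or decision uses it. Confidence is also summarised by means, standard deviations and a mixed model, and an analyst could add another coefficient later from the same data. All of that stands and limits the weight of the point. It does not supply an agreement measure by modality that respects the order of the scores.

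A reader might infer two stronger claims, and neither is supported:

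- **That Fleiss' kappa will report poor agreement whenever scores are nearly identical.** The documents give no reader scatter. If 10-20% of reads are one step off, the coefficient is lowered but not poor. Low values need roughly 40% or more of reads to miss the case value.
- **That the modality comparison would mainly reflect how many scale steps readers use.** On a fixed case mix (all 11 levels), Fleiss' kappa moves from 0.65 to 0.31 as scatter rises from 20% to 67%. Narrowing the case range to 70-100% moves it only from 0.65 to 0.60 at 20% scatter and from 0.31 to 0.20 at 67%. So with one-step errors it mainly tracks scatter.

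The alternatives have weaknesses too. At 50% scatter the same narrowing lowers the ICC from 0.95 to about 0.7, against 0.36 to 0.27 for Fleiss' kappa. With case values at 90 or 100% and 20% scatter the two nearly coincide (0.58 and 0.52). An ICC on the raw percentage would also count '90%, yes' and '90%, no' as perfect agreement. These objections stand and shape the remedy, but they do not make a nominal statistic suitable for ordered scores.

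**Conclusion.** The point holds for confidence and image quality only. That unweighted Fleiss' kappa gives no credit for near agreement is a property of the statistic and needs no assumption about the data. Its value of about 0.33 for gaps of 1, 3 and 5 steps illustrates this for one pattern of disagreement.

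How far it understates near agreement is conditional. The ranges above rest on assumed one-step errors, assumed case mixes, 50 patients and five readers. They run from mild attenuation to values near 0.1. The consequence is limited to a descriptive comparison, so this is a worthwhile improvement and not a threat to the trial's main results. Fleiss' kappa is appropriate for the presence and location items.

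**What to change.** Amend the agreement paragraph of section 7.3 as follows:

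- Keep Fleiss' kappa for whether, and where, a hemorrhage or fracture is seen.
- For image quality, report a quadratic-weighted multi-rater kappa, or Krippendorff's ordinal alpha.
- For confidence, report a two-way random-effects ICC for absolute agreement. Compute it on a score that combines the yes/no call with its percentage, for example signed confidence (+90 for yes at 90%, -90 for no at 90%), so that opposite calls do not count as agreement.
- Give each coefficient by modality with a bootstrap confidence interval that resamples patients.
- Report the score distributions by modality alongside, because all these coefficients depend on the spread of scores, and a difference between modalities could come from spread alone.

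The cost is a change of wording and a little extra analysis work. No new data are needed.

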## **8.0 STUDY MANAGEMENT**

### **8.1 Institutional Review Board (IRB) Approval and Consent**

It is expected that the IRB will have the proper representation and function in accordance with federally mandated regulations. The IRB should approve the consent form and protocol.

In obtaining and documenting informed consent, the investigator should comply with the applicable regulatory requirement(s), and should adhere to Good Clinical Practice (GCP) and to ethical principles that have their origin in the Declaration of Helsinki.

Before recruitment and enrollment onto this study, the patient will be given a full explanation of the study and will be given the opportunity to review the consent form. Each consent form must include all the relevant elements currently required by the FDA Regulations and local or state regulations. Once this essential information has been provided to the patient and the investigator is assured that the patient understands the implications of participating in the study, the patient will be asked to give consent to participate in the study by signing an IRB-approved consent form.

Prior to a patient's participation in the trial, the written informed consent form should be signed and personally dated by the patient and by the person who conducted the informed consent discussion.

## **8.2 Registration Procedures**

Study participants will be registered into REDCap®, a web based clinical research platform by one of the Study Coordinators.

## **8.3 Data Management**

### **8.3.1 Data Collection and Documentation**

We will utilize TBI CDE to document the imaging data of patients for data analysis purposes. The online REDCap software system provided by UNC's TraCS Institute will be used for data collection and management, which will ensure that data collected are consistent and follow standardized coding. Data will be entered into REDCap by the study coordinator within 5 business days.

All data requested on the case report forms (CRFs) will be recorded by the study coordinator. All missing data will be explained. If a space on the CRF is left blank because the procedure was not done or the question was not asked, the study team will write "N/D". If the item is not applicable to the individual case, the study team will write "N/A". Every attempt will be made to ensure that there is as little missing data as possible including reminder phone calls and follow-up phone calls, if a subject misses a visit. However, this study is limited to a single subject visit so missing values will be minimal. If subjects withdraw, the reason for subject withdrawal will be documented in the study database.

### **8.3.2 Data Quality**

The study team will adhere to the Department of Radiology Internal Monitoring and Quality Assurance Standard Operating Procedures to ensure data quality, completeness, and accuracy are maintained for this study. The Department of Radiology's Internal Quality Assurance program will verify a random selection of at least 25% of all source documents for accuracy and completeness.

### **8.3.3 Data and Safety Monitoring**

This study will not have a data and safety monitoring board. The principal investigator will maintain overall responsibility for data and safety monitoring.

Safety Monitoring will be performed by a licensed physician who is not a study investigator. Medical monitoring will occur at least annually for the duration of this study.

The research coordinator will monitor the study files on a monthly basis to ensure the appropriate regulatory and IRB documentations are on file and up to date. The research coordinator will also be responsible for ensuring proper study documentation in order to verify compliance with Institutional policy, IRB, FDA and GCP guidelines in the following areas: Informed consent, Protocol, Source Documents and Electronic Case Report Forms.

The principal investigator and research coordinator will be responsible for maintaining IRB correspondence. IRB approved forms maintained, as part of the study will include the subject consent form and the HIPAA authorization form.

The investigator will permit study-related monitoring, audits, and inspections by the Research Quality Assurance Office, IRB, and government regulatory bodies, of all study related documents (e.g. source documents, regulatory documents, data collection instruments, study data etc.). The investigator will ensure the capability for inspections of applicable study-related facilities (e.g. pharmacy, diagnostic laboratory, etc.)

#### **8.3.4 Data archival and data sharing**

Data from this study may be submitted to the Federal Interagency Traumatic Brain Injury (FITBIR) informatics system. FITBIR is a computer system run by the National Institutes of Health that allows researchers studying traumatic brain injury to collect and share information with each other.

### **8.4 Adherence to the Protocol**

Except for an emergency situation in which proper care for the protection, safety, and well-being of the study patient requires alternative treatment, the study shall be conducted exactly as described in the approved protocol.

#### **8.4.1 Emergency Modifications**

UNC investigators may implement a deviation from, or a change of, the protocol to eliminate an immediate hazard(s) to trial subjects without prior UNC's IRB/IEC approval/favorable opinion.

For any such emergency modification implemented, an IRB modification form must be completed by UNC Research Personnel within five (5) business days of making the change.

#### **8.4.2 Protocol Deviations/Violations**

According to UNC's IRB, a protocol deviation is any unplanned variance from an IRB approved protocol that:

- Is generally noted or recognized after it occurs
- Has no substantive effect on the risks to research participants
- Has no substantive effect on the scientific integrity of the research plan or the value of the data collected
- Did not result from willful or knowing misconduct on the part of the investigator(s).

An unplanned protocol variance is considered a violation if the variance meets any of the following criteria:

- Has harmed or increased the risk of harm to one or more research participants.
- Has damaged the scientific integrity of the data collected for the study.

- Results from willful or knowing misconduct on the part of the investigator(s).
- Demonstrates serious or continuing noncompliance with federal regulations, State laws, or University policies.

If a deviation or violation occurs please follow the guidelines below:

**Protocol Deviations:** Deviations should be summarized and reported to the IRB at the time of continuing review.

**Protocol Violations:** Violations should be reported by UNC personnel within one (1) week of the investigator becoming aware of the event using the same IRB online mechanism used to report Unanticipated Problems.

**Unanticipated Problems:**

Any events that meet the criteria for “Unanticipated Problems” as defined by UNC’s IRB must be reported by the study team using the IRB’s web-based reporting system.

#### **8.5 Amendments to the Protocol**

Should amendments to the protocol be required, the amendments will be originated and documented by the Principal Investigator at UNC. It should also be noted that when an amendment to the protocol substantially alters the study design or the potential risk to the patient, a revised consent form might be required.

The written amendment, and if required the amended consent form, must be sent to UNC’s IRB for approval prior to implementation.

#### **8.6 Record Retention**

Study documentation includes all eCRFs, data correction forms or queries, source documents, essential correspondence, monitoring logs/letters, and regulatory documents (e.g., protocol and amendments, IRB correspondence and approval, signed patient consent forms).

Source documents include all recordings of observations or notations of clinical activities and all reports and records necessary for the evaluation and reconstruction of the clinical research study.

Government agency regulations and directives require that all study documentation pertaining to the conduct of a clinical trial must be retained by the study investigator. In the case of a study with a drug seeking regulatory approval and marketing, these documents shall be retained for at least two years after the last approval of marketing application in an International Conference on Harmonization (ICH) region. In all other cases, study documents should be kept

on file until three years after the completion and final study report of this investigational study.

#### **8.7 Obligations of Investigators**

The Principal Investigator is responsible for the conduct of the clinical trial at the site in accordance with Title 21 of the Code of Federal Regulations and/or the Declaration of Helsinki. The Principal Investigator is responsible for personally overseeing the treatment of all study participants. The Principal Investigator must assure that all study site personnel, including sub-investigators and other study staff members, adhere to the study protocol and all FDA/GCP/NCI regulations and guidelines regarding clinical trials both during and after study completion.

